## Risks

### ***Bleeding-related events***

There have been reports of hemorrhagic events in subjects treated with ibrutinib both with and without thrombocytopenia. These include primarily minor hemorrhagic events such as contusion; epistaxis; and petechiae; and some major hemorrhagic events including gastrointestinal bleeding; intracranial hemorrhage; and hematuria. Use of ibrutinib in subjects requiring other anticoagulants or medications that inhibit platelet function may increase the risk of bleeding.

### ***Leukostasis***

There were isolated cases of leukostasis reported in subjects treated with ibrutinib. A high number of circulating lymphocytes ( $> 400,000/\mu\text{L}$ ) may confer increased risk. Consider temporarily holding ibrutinib. Subjects should be closely monitored. Administer supportive care including hydration and/or cytoreduction as indicated.

### ***Lymphocytosis***

Upon initiation of treatment, a reversible increase in lymphocyte counts (ie,  $\geq 50\%$  increase from baseline and an absolute count  $> 5000/\mu\text{L}$ ), often associated with reduction of lymphadenopathy, has been observed in most subjects with chronic lymphocytic leukemia (CLL) or small lymphocytic lymphoma (SLL) treated with ibrutinib. This effect has also been observed in some subjects with mantle cell lymphoma (MCL).

treated with ibrutinib. This observed lymphocytosis is a pharmacodynamic effect and should not be considered progressive disease in the absence of other clinical findings. In both disease types, lymphocytosis typically occurs during the first few weeks of ibrutinib therapy (median time 1.1 weeks) and typically resolves within a median of 8.0 weeks in subjects with MCL and 18.7 weeks in subjects with CLL/SLL.

A large increase in the number of circulating lymphocytes (eg,  $> 400,000/\mu\text{L}$ ) has been observed in some subjects. Lymphocytosis was not commonly observed in subjects with Waldenström's macroglobulinemia treated with ibrutinib. Lymphocytosis appeared to occur in lower incidence and at lesser magnitude in subjects with CLL/SLL receiving ibrutinib in combination with chemoimmunotherapy.

### ***Atrial Fibrillation***

Atrial fibrillation and atrial flutter have been reported in subjects treated with ibrutinib, particularly in subjects with cardiac risk factors, hypertension, acute infections, and a previous history of atrial fibrillation. For atrial fibrillation which persists, consider the risks and benefits of ibrutinib treatment and follow the protocol dose modification guidelines (see Section 6).

### ***Cytopenias***

Treatment-emergent Grade 3 or 4 cytopenias (neutropenia, thrombocytopenia, and anemia) were reported in subjects treated with ibrutinib.

### ***Diarrhea***

Diarrhea is the most frequently reported non-hematologic AE with ibrutinib monotherapy and combination therapy. Other frequently reported gastrointestinal events include nausea, vomiting, and constipation. These events are rarely severe. Should symptoms be severe or prolonged follow the protocol dose modification guidelines (see Section 6).

### ***Infections***

Fatal and non-fatal infections have occurred with ibrutinib therapy. At least 25% of subjects with MCL and 35% of subjects with CLL had Grade 3 or greater infections per NCI Common Terminology Criteria for Adverse Events (CTCAE v4.0). The most commonly reported infections include pneumonia, cellulitis, urinary tract infection and sepsis. Although causality has not been established, cases of progressive multifocal leukoencephalopathy (PML) have occurred in subjects treated with ibrutinib. Cases of hepatitis E, which may be chronic, have occurred in patients treated with ibrutinib. Subjects should be monitored for signs and symptoms (such as fever, chills, weakness, confusion, vomiting and jaundice, and abnormal liver function tests) and appropriate therapy should be instituted as indicated.

### ***Lymphocytosis***

Upon initiation of treatment, a reversible increase in lymphocyte counts (ie,  $\ge 50\%$  increase from baseline and an absolute count  $> 5,000/\mu\text{L}$ ), often associated with reduction of lymphadenopathy, has been observed in most subjects with CLL/SLL

treated with ibrutinib. This effect has also been observed in some subjects with MCL treated with ibrutinib. This observed lymphocytosis is a pharmacodynamic effect and should not be considered progressive disease in the absence of other clinical findings. In both disease types, lymphocytosis typically occurs during the first few weeks of ibrutinib therapy (median time 1.1 weeks) and typically resolves within a median of 8.0 weeks in subjects with MCL and 18.7 weeks in subjects with CLL/SLL.

A large increase in the number of circulating lymphocytes (eg, > 400,000/ $\mu$ L) has been observed in some subjects. Lymphocytosis was not observed in subjects with WM treated with ibrutinib. Lymphocytosis appeared to occur in lower incidence and at lesser magnitude in subjects with CLL/SLL receiving ibrutinib in combination with chemoimmunotherapy.

### ***Non-Melanoma Skin Cancer***

Non-melanoma skin cancers have occurred in subjects treated with ibrutinib. Monitor subjects for the appearance of non-melanoma skin cancer.

### ***Rash***

Rash has been commonly reported in subjects treated with either single-agent ibrutinib or in combination with chemotherapy. Rash occurred at a higher rate in the ibrutinib arm than in the ofatumumab arm in Study 1112. Most rashes were mild to moderate in severity.

### ***Tumor lysis syndrome (TLS)***

There have been reports of tumor lysis syndrome (TLS) events in subjects treated with single-agent ibrutinib or in combination with chemotherapy. Subjects at risk of tumor lysis syndrome are those with comorbidities and/or risk factors such as high tumor burden prior to treatment, increased uric acid (hyperuricemia), elevated lactate dehydrogenase (LDH), bulky disease at baseline, and pre-existing kidney abnormalities.

### ***Interstitial Lung Disease (ILD)***

Cases of interstitial lung disease (ILD) have been reported in subjects treated with ibrutinib. Monitor subjects for pulmonary symptoms indicative of ILD. Should symptoms develop, follow the protocol dose modification guidelines (see [Section 6](#)).

## **5.2 Availability**

Ibrutinib will be provided for this clinical trial by its manufacturer, Pharmacyclics.

## **5.3 Agent Ordering**

Each study site will order their drug stock through Pharmacyclics. Ibrutinib will be requested from the research pharmacy at each study site.

## **5.4 Agent Accountability**

Ibrutinib will be kept secure according to institutional guidelines and will be processed and dispensed by Investigational Drug Services at Stanford University and by analogous services at outside collaborating centers.

### **Overdose**

Any dose of study drug in excess of that specified in this protocol is considered to be an overdose. Signs and symptoms of an overdose that meet any Serious Adverse Event criterion must be reported as a Serious Adverse Event in the appropriate time frame and documented as clinical sequelae to an overdose.

There is no specific experience in the management of ibrutinib overdose in subjects. No maximum tolerated dose (MTD) was reached in the Phase 1 study, in which subjects received up to 12.5 mg/kg/day (1,400 mg/day). Healthy subjects were exposed up to single dose of 1,680 mg. One healthy subject experienced reversible Grade 4 hepatic enzyme increases (AST and ALT) after a dose of 1,680 mg. Subjects who ingest more than the recommended dosage should be closely monitored and given appropriate supportive treatment.

Refer to Section 7.2 for further information regarding AE reporting.

## **6. DOSE MODIFICATIONS**

The study dose levels of ibrutinib are defined as follows.

- Dose level 0: 420 mg orally once a day.
- Dose level -1: 280 mg orally once a day.
- Dose level -2: 140 mg orally once a day.
- Dose level -3: Discontinue ibrutinib.

The dose of ibrutinib should be modified according to the dose modification guidelines in Table 2 if any of the following toxicities occur and are considered to be due to ibrutinib.

### **Hematologic Adverse Events**

- Grade 3 ANC (< 1,000/  $\mu$ L) with an associated temperature  $\geq 38.5^{\circ}\text{C}$
- Grade 4 ANC (< 500/ $\mu$ L) for more than 7 days
- Grade 3 thrombocytopenia (< 50,000/ $\mu$ L) in the presence of Grade  $\geq 2$  bleeding events
- Grade 4 thrombocytopenia (< 25,000/ $\mu$ L)

### **Non-Hematologic Adverse Events**

- Grade 3 or 4 nausea, vomiting, or diarrhea if persistent, despite optimal anti-emetic and/or anti-diarrheal therapy
- Any other Grade 4 or unmanageable Grade 3 toxicity attributed to ibrutinib

**Table 2: Ibrutinib Dose Modifications**

Hematologic Adverse Events	
Occurrence	Action to be Taken
First	Withhold ibrutinib until recovery to an ANC $\geq$ 750 or platelets $>$ 25,000 with no evidence of Grade $\geq$ 2 bleeding; may restart at original dose level
Second	Withhold ibrutinib until recovery to an ANC $\geq$ 750 or platelets $>$ 25,000 with no evidence of Grade $\geq$ 2 bleeding; may restart at 1 dose level lower
Third	Withhold ibrutinib until recovery to an ANC $\geq$ 750 or platelets $>$ 25,000 with no evidence of Grade $\geq$ 2 bleeding; may restart at 1 dose level lower
Fourth	Discontinue ibrutinib a
Non-Hematologic Adverse Events	
First	Withhold ibrutinib until recovery to Grade $\leq$ 1 or baseline; may restart at original dose level
Second	Withhold ibrutinib until recovery to Grade $\leq$ 1 or baseline; may restart at 1 dose level lower
Third	Withhold ibrutinib until recovery to Grade $\leq$ 1 or baseline; may restart at 1 dose level lower
Fourth	Discontinue ibrutinib a

a If ibrutinib is discontinued for toxicity, subject will end the Treatment Phase of the study.

Dose changes must be recorded. At the Investigator's discretion, the dose of ibrutinib may be re-escalated after 8 weeks of a dose reduction in the absence of a recurrence of the toxicity that led to the reduction.

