### **3.1.2 Inclusion criteria (prior to ibrutinib administration)**

- Age  $\geq$  18 years
- Adequate hematologic function, defined as ANC  $> 0.75 \times 10^9/L$ ; platelet count  $> 50 \times 10^9/L$ ; and hemoglobin  $> 8.0 \text{ g/dL}$  without transfusion or growth-factor support for at least 7 days prior to screening (with the exception of pegylated G-CSF and darbopoietin, which require at least 14 days of abstinence prior to screening)
- Adequate hepatic and renal function, as defined by serum AST and ALT  $\leq 3.0 \times$  upper limit of normal (ULN); estimated creatinine clearance  $\geq 30 \text{ mL/min}$  via Cockroft-Gault formula; and bilirubin  $\leq 1.5 \times$  ULN (unless elevated bilirubin is due to Gilbert's syndrome or of non-hepatic origin)
- Adequate coagulation studies, defined as PT/INR and PTT (aPTT)  $\leq 1.5 \times$  ULN
- Female subjects who are of non-reproductive potential (ie, post-menopausal by history - no menses for  $\geq 1$  year; OR history of hysterectomy; OR history of bilateral tubal ligation; OR history of bilateral oophorectomy). Female subjects of childbearing potential must have a negative serum pregnancy test upon screening.
- Male and female subjects who agree to use both a highly effective method of birth control (eg, implants; injectables; combined oral contraceptives; some intrauterine devices [IUDs]; sexual abstinence; or sterilized partner) and a barrier method (eg, condoms; vaginal ring; sponge; etc) during the period of therapy and for 30 days after the last dose of study drug for females and 90 days after the last dose of the study drug for males.
- Between Day +60 and Day +90 after allogeneic HCT

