#### **3.2.2 Exclusion Criteria (prior to ibrutinib administration)**

- Active and uncontrolled acute GvHD Grades III or IV
- Use of secondary therapy for acute GvHD at any time (defined as any systemic therapy intended to treat acute GvHD besides corticosteroids)
- Requirement for anticoagulation with warfarin or other Vitamin K antagonists (concomitant use of other anticoagulants is permitted)
- Relapsed leukemia (> 5% leukemic blasts in peripheral blood or bone marrow after allogeneic HCT)
- Karnofsky Performance Status < 60%
- Chemotherapy  $\leq$  21 days prior to first administration of study treatment and/or monoclonal antibody  $\leq$  6 weeks prior to first administration of study treatment
- Vaccinated with live, attenuated vaccines within 4 weeks of first dose of study drug.
- Currently active, clinically significant cardiovascular disease, such as uncontrolled arrhythmia or Class 3 or 4 congestive heart failure as defined by the New York Heart Association Functional Classification; or a history of myocardial infarction, unstable angina, or acute coronary syndrome within 6 months prior to randomization.

- History of stroke or intracranial hemorrhage within 6 months prior to screening
- Any life-threatening illness, medical condition, or organ system dysfunction that, in the investigator's opinion, could compromise the subject's safety or put the study outcomes at undue risk.
- Major surgery within 4 weeks of first dose of study drug.
- Any uncontrolled active systemic infection.
- Unresolved toxicities from prior anti-cancer therapy, defined as having not resolved to Common Terminology Criteria for Adverse Event (CTCAE, version 4), Grade ≤ 1, or to the levels dictated in the inclusion/exclusion criteria with the exception of alopecia
- Unable to swallow capsules or malabsorption syndrome, disease significantly affecting gastrointestinal function, or resection of the stomach or small bowel, symptomatic inflammatory bowel disease or ulcerative colitis, or partial or complete bowel obstruction
- Requires treatment with a strong cytochrome P450 (CYP) 3A4/5 inhibitor (see Appendix E).
- Unwilling or unable to participate in all required study evaluations and procedures.
- Unable to understand the purpose and risks of the study and to provide a signed and dated informed consent form (ICF) and authorization to use protected health information (in accordance with national and local subject privacy regulations).

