#### **6.1 Treatment Discontinuation**

Study treatment with ibrutinib will be permanently discontinued for any subject if any of the following occur.

- Grade 4 treatment related (ie, possibly-, probably-, or definitely-related) non-hematologic toxicity
- Grade 4 neutropenia lasting > 21 days
- Grade 4 thrombocytopenia lasting > 21 days or associated with clinically significant bleeding (requiring > 3 units of packed red blood cells within 24 hours)

to replace loss OR bleeding from a site which in the Investigator's opinion is a potential life-threatening source irrespective of blood loss)

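### Table 2 lets a febrile subject with ANC 750–999/µL meet the ibrutinib restart test at the moment the hold begins

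*Combined protocol and SAP*

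**What the plan says.** Section 6 (Dose Modifications) applies Table 2 "if any of the following toxicities occur and are considered to be due to ibrutinib". The list under Hematologic Adverse Events has four triggers. Two are counts alone: ANC below 500/µL for more than 7 days, and platelets below 25,000/µL. The other two pair a count with a clinical sign. One is ANC below 1,000/µL "with an associated temperature" of at least 38.5 °C. The other begins "Grade 3 thrombocytopenia (< 50,000" and adds bleeding of Grade 2 or worse.

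Table 2 uses one recovery test for the first, second and third occurrence: "Withhold ibrutinib until recovery to an ANC $\geq$ 750 or platelets $>$ 25,000 with no evidence of Grade $\geq$ 2 bleeding". After the first occurrence the original dose may be resumed, after the second and third the dose drops one level, and at the fourth the drug stops.

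The ANC figure has a counterpart at first dosing. Section 3.1.2 asks for "Adequate hematologic function, defined as ANC" above 0.75 × 10⁹/L. Section 3.2.2 sets an infection exclusion alongside it: "Any uncontrolled active systemic infection".

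**The concern.** A hold rule should state what must improve before the drug is resumed. For febrile neutropenia between 750 and 999/µL, the only figure given for recovery is already met when the hold is imposed, and the fever that made the count a trigger is not mentioned again.

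The cut-off of 750 is not in dispute, since it agrees with the level accepted at first dosing. What is missing is the clinical half of the condition. The same row supplies that half for bleeding. Other holds also ask for improvement: non-hematologic toxicity must return to Grade 1 or baseline (Table 2), hepatic impairment to Child-Pugh A or better (Section 6), and a subject held for new anticoagulation must be stable without bleeding (Section 4.1).

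Subjects start the drug 60 to 90 days after an allogeneic transplant. Section 5.1 reports fatal infections on ibrutinib and lists febrile neutropenia among the more frequent serious events. At stake is a restart during unresolved febrile neutropenia that the protocol's wording permits, with room for sites to read the rule differently.

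**Working it through.** The plan states no figure for this point, so the check is whether each hold trigger can still be true when the recovery test is true. Trigger thresholds come from the Hematologic Adverse Events list in Section 6 and recovery thresholds from Table 2. Table 2 gives no unit; I read per µL, as in the trigger list. On that scale the Section 3.1.2 start criterion of 0.75 × 10⁹/L is 750/µL.

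With each recovery threshold applied to the cell line that fell:

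| Hold trigger | Recovery count | Counts satisfying both | Closed by another term? |
|---|---|---|---|
| ANC < 1,000 and temperature ≥ 38.5 °C | ANC ≥ 750 | 750–999 | No |
| ANC < 500 for > 7 days | ANC ≥ 750 | None | Not needed |
| Platelets < 50,000 and Grade ≥ 2 bleeding | Platelets > 25,000 | 25,001–49,999 | Yes, by the no-bleeding term |
| Platelets < 25,000 | Platelets > 25,000 | None | Not needed |

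The open band has width 1,000 − 750 = 250/µL, or 999 − 750 + 1 = 250 integer values. One of the four triggers can persist through recovery. Of the two that pair a count with a sign, one has the sign carried into recovery and one does not.

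**Other readings of the row.** On the strictest reading (ANC ≥ 750, platelets > 25,000 and no Grade ≥ 2 bleeding, all required), a subject at 39 °C with ANC 900, platelets 60,000 and no bleeding passes, so the band stays open. On the literal *or*, that subject passes at any ANC from 0 to 999, because the platelet count alone suffices. That is a separate, wider ambiguity, and the point does not depend on it.

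**Other rules that might fill the gap.**
- The infection exclusion in Section 3.2.2 applies before the first dose, not at restart.
- The non-hematologic list covers "Any other Grade 4 or unmanageable Grade 3 toxicity attributed to ibrutinib", and Section 6.1 ends treatment for "Grade 4 treatment related (ie, possibly-, probably-, or definitely-related) non-hematologic toxicity". These reach a severe attributed infection but not fever without such an event.
- The neutropenia stopping rule in Section 6.1 concerns Grade 4 (below 500/µL) for more than 21 days, so it does not reach 750–999.

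**With the repair.** Restart would require (ANC ≥ 750 and temperature < 38.5 °C) or ANC ≥ 1,000. The trigger requires ANC < 1,000 and temperature ≥ 38.5 °C. The first limb contradicts the temperature part and the second contradicts the count part, so the overlap is empty: 0 of 4 triggers instead of 1 of 4.

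**The case against.** The best reply is that the table speaks of *recovery*, and a subject still at 39 °C with ANC 900 has not recovered in any ordinary sense. Restart is optional, and investigator decision can end treatment (Section 4.2). Resuming with the trigger unchanged would call for another hold, which can count as the next occurrence and move the subject down the dose ladder. These points stand, and they limit the likely harm. They do not repair the rule: the same words govern the bleeding trigger, and there the condition was still written out.

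A second reply is that the asymmetry may be deliberate. Bleeding is a recognized ibrutinib risk with its own monitoring in Section 12.2, whereas Section 7.2 treats febrile episodes as common after transplant. Tying restart to fever could prolong holds for unrelated causes. That is a real cost, but the trigger applies only to events already attributed to ibrutinib. The ANC ≥ 1,000 limb of the repair also limits such holds, because at that count the trigger no longer applies.

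That limb draws a fair criticism of its own: it would let a subject restart at ANC 1,000 while still febrile. The repair makes restart consistent with the trigger and does not claim to be a full infection check.

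It is also true that the exposed group is narrow, that uncontrolled infection in Section 3.2.2 is not the same thing as fever, and that the documents do not demonstrate differing practice between sites. Quarterly safety calls with site investigators (Section 11.2) would help there.

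**Conclusion.** The concern holds. For ANC 750–999/µL with a temperature of 38.5 °C or more, the hold trigger and the restart test are true together, and no other rule in the protocol requires the fever to resolve. This assumes that the event is attributed to ibrutinib, platelets exceed 25,000/µL, there is no Grade 2 or worse bleeding, and no separately governed severe toxicity is present.

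The 250/µL band and the count of one trigger in four measure the gap in the rule, not a frequency or a risk. The number of subjects affected cannot be derived from the documents. The intention-to-treat primary analysis, sample size and error rates do not change. This is a moderate safety-rule defect that should be corrected.

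**What to change.** In the three hematologic restart rows of Table 2, add for the febrile-neutropenia trigger: restart only when ANC is at least 750/µL and temperature is below 38.5 °C, or when ANC is at least 1,000/µL. All of these figures are already in Section 6. How long the temperature must stay down is a clinical choice the documents do not settle; 24 to 48 hours is an assumed range from which the sponsor could choose.

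In the same edit, as a clarification, tie each threshold to the affected cell line: ANC for neutropenia, platelets above 25,000/µL without Grade 2 or worse bleeding for thrombocytopenia, and both if both fell.

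The cost is amendment wording in one table. Some holds would last longer, which slightly lowers exposure. A few could pass the limit of 28 continuous days of interruption in Section 4.2 and so lead to withdrawal from study treatment.

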#### **Dose modifications for use with CYP3A inhibitors**

Concomitant use of strong CYP3A inhibitors which would be taken chronically (eg, ritonavir; indinavir; nelfinavir; saquinavir; boceprevir; telaprevir; nefazodone) is not recommended. For short-term use (treatment for 7 days or less) of strong CYP3A inhibitors (eg, antifungals and antibiotics) either reduce ibrutinib dose to 140 mg daily or withhold ibrutinib therapy until the CYP3A inhibitor is no longer needed.

Reduce ibrutinib dose to 140 mg orally once daily if a moderate CYP3A inhibitor must be used (eg, fluconazole; darunavir; erythromycin; diltiazem; atazanavir; aprepitant; amprenavir; fosamprevir; crizotinib; imatinib; verapamil; and ciprofloxacin). Subjects taking concomitant strong or moderate CYP3A inhibitors should be monitored more closely for signs of ibrutinib toxicity.

**As most study subjects are expected to be receiving azoles (fluconazole; voriconazole; posaconazole) until at least Day +75 after allogeneic HCT, the dose of ibrutinib will be 140 orally once daily while on such medications.** Once these agents are stopped, the dose may be escalated to 420 mg once daily.

